3. STUDY DESIGN

During the grant application process, all relevant stakeholders were involved in setting up this study protocol during a co-creation process. The co-creation team consisted of representatives from patient associations, healthcare insurers, the knowledge institute of the federation of medical specialists, the national healthcare institute, methodological and statistical expertise, the Netherlands Orthopaedic Association (NOV), the ZE&GG program for appropriate healthcare, and the project team. ZE&GG organized meetings to discuss crucial points with the stakeholders, which resulted in a well-considered research protocol approved by all involved stakeholders. The NOV signed a declaration of support and commits to implementation of the results.

In this study a randomized controlled trial with 3 arms will be performed. Patients will be randomized 1:1:1 in the following groups:

[figure not shown]
1. RFU: routine follow-up at 10 years after THA or TKA (control)
2. Active COD: No RFU at 10 years. Patients will be informed about the study and complete questionnaires. Check-ups are scheduled only on demand by the patient or health care professional (HCP) (intervention)
3. Passive COD: No RFU at 10 years. Patients will not be informed about the study to avoid any trigger to contact a HCP and will not complete questionnaires (intervention)

Patients will be followed for 1 year after RFU or COD (11 years after surgery). Informing the patients about the study and letting them complete questionnaires might result in trigger bias to contact a HCP. Therefore, patients in the intervention group will be divided into two groups: 1) one group will be informed about the study and complete questionnaires (active COD), 2) the other group will not be contacted and informed about the study to avoid trigger bias (passive COD). Of the latest group, only data from the LROI and EPD will be used. The control group will receive RFU at 10 years after THA or TKA and will complete questionnaires. Both groups completing questionnaires (active COD and RFU group) will be actively asked to participate in the study and to complete questionnaires and therefore will be randomized after informed consent.

A total of 10 hospitals will participate in the study. As randomization will be on individual patient level, all centers will perform both RFU and COD. Some centers will therefore perform RFU at 10 years while they already discontinued RFU, while other centers will have to implement COD while their current practice is RFU.

Patients will be included using the Dutch Arthroplasty Register and the EPD. The period of inclusion will be 18 months. The total study duration will be 30 months.

Figure 1: Overview of the study design.

4. STUDY POPULATION

4.1 Population (base)

Patients will be identified using the LROI register and the EPD. In 2015, 28,872 THA and 24,244 TKA were performed in the Netherlands [3]. The participating centres indicated that they performed between 400 and 800 THA and TKA per year. Taking into account a mortality rate of 16% 10 years after THA or TKA [18, 19], a revision rate of 6% 10 years after THA and TKA [3] and that 33% of the patients might not want to participate, the patient population will still be large enough to obtain our required sample size.

4.2 Inclusion criteria

In order to be eligible to participate in this study, a participant must meet all of the following criteria:

- Underwent primary THA or TKA approximately 10 years ago
- Age 50 years or older at time of THA or TKA
- Capable and willing to complete questionnaires (when applicable)
- Understanding Dutch or English
- Willing to provide written informed consent in case the patient will complete questionnaires

4.3 Exclusion criteria

A potential participant who meets any of the following criteria will be excluded from participation in this study:

- Other indication for surgery than osteoarthritis
- Surgery was bilateral
- Deceased
- Revision arthroplasty of hip or knee, except a conversion from unicompartmental knee arthroplasty to TKA or from hip hemiarthroplasty/resurfacing to THA
- Already participating in this study due to another hip or knee surgery

4.4 Sample size calculation

We carefully determined the required number of patients to ensure reliable outcome estimates in collaboration with co-creating stakeholders and by consulting orthopaedic surgeons using an online survey on what constitutes convincing evidence. The agreed sample size is 250 patients per group. Therefore, we plan to randomize 250 patients per study group resulting in a total of 750 THA and 750 TKA patients.

To provide a rough indication of the statistical power, we used the online power calculator tool available on Sealed Envelope [20]. The sample size calculation is based on the comparison of RFU vs. active COD as the primary analysis. For this calculation, we assumed that the actual complication rate in both groups is 10%. With the agreed number, it is possible to detect a clinical relevant difference of 10% in complications between the two groups. If there is truly no difference between active COD and RFU, 190 patients per group are needed to be 80% sure that the limits of a two-sided 95% confidence interval will exclude a difference between active COD and RFU of more than 10%. Anticipating 20-25% loss to follow up, we plan to randomize 250 patients.

5. TREATMENT OF RESEARCH PARTICIPANTS

This study will compare COD and RFU at 10 years after THA and TKA, both of which are currently used in clinical settings, as confirmed by the Dutch Orthopaedics Society (NOV). In recent years, some hospitals discontinued RFU at 10 years for various reasons, thereby deviating from the Dutch guidelines. In many cases, patients were not personally informed about these policy changes.

Check-ups on demand (COD) are scheduled only at request of the patient or health care professional (HCP). Patients are welcome to contact a HCP (i.e. general practitioner, physical therapist or hospital) in case of pain, concerns or other symptoms at any time (consistent with current standard care practices).

COD will be compared to RFU at 10 years after THA and TKA. RFU consists of an evaluation by an orthopaedic surgeon or resident and an X-ray. In case of concerns, a physical examination will be conducted. In the meantime, patients are still welcome to contact a HCP (i.e. general practitioner, physical therapist or hospital) in case of pain, concerns or other symptoms at any time (consistent with current standard care practices).

6. INVESTIGATIONAL PRODUCT

NA

7. NON-INVESTIGATIONAL PRODUCT

NA

8. METHODS

8.1 Study parameters/endpoints

8.1.1 Main study parameter/endpoint

Clinical endpoint:

- Number and type of complications
Described as unplanned, unexpected and undesired outcomes related to THA or TKA that are directly associated with the care or services provided to the patient (i.e. knee- or hip related complaints or changes on X-ray that lead to extra FU, a referral to another specialism or (surgical) intervention) (like infection, peri-prosthetic fracture, loosening, malalignment or malposition of components, prosthetic wear, dislocation, etc)

Process endpoint:

- Healthcare consumption related to THA and TKA FU (number of X-rays and clinical visits)

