1. INTRODUCTION AND RATIONALE

Clinical Dutch guidelines recommend routine follow-up (RFU) consisting of an X-ray and clinical visit within 3 months and at 1 year after total hip arthroplasty (THA) and total knee arthroplasty (TKA) [1, 2]. RFU after 5 years (THA) or every 5 years (TKA) might also be worth considering. However, the added value of RFU can be questioned, as registry data show excellent survival after THA and TKA [3] and revisions are rare and seldom without symptoms [4-7]. Currently, clinical practice demonstrates significant variation in RFU, as some hospitals have already decided to discontinue RFU and instead perform check-ups only upon the request (COD) of the patient or orthopedic surgeon. This practice variation was confirmed by a national survey performed in 2019 among orthopaedic surgeons (non-published results). So, both RFU and COD are currently used in clinical practice, which is also acknowledged by the Dutch Orthopaedic Society (NOV).

There is equipoise among orthopaedic surgeons; a widely shared feeling of genuinely not knowing what the best course of action is. What is the risk of missing a complication? Do patients report issues promptly? For example, osteolysis (break down of bone tissue) and wear of the prosthesis can occur without symptoms. When discovered early, this can be monitored and managed by a relatively simple revision surgery. However, when discovered late, this can result in catastrophic failure (i.e. unexpected and unannounced failing of the prostheses with large consequences) and therefore a more complex revision surgery, with higher costs and more risks for the patient. There is willingness to adjust clinical practice, but also hesitation due to the risks of providing suboptimal care and missing a complication at the long term. In other words, replacing RFU with only COD might not be without risks, i.e. missed complications, reduced patient satisfaction or physical function.

Current guideline recommendations are of low level evidence. Both guidelines suggest that the added value of RFU is likely limited, but convincing research is lacking [1, 2].

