8.3 Study procedures

This study will be conducted in 10 Dutch hospitals across the Netherlands. Patients will be recruited using the LROI register and EPD. After inclusion, baseline characteristics will be obtained from the EPD and LROI register. Information on patient background will be collected to explore potential differences in follow-up needs, including among patients with different ethnic backgrounds. Previous research shows that people with a migrant background visit specialists and hospitals less often than native Dutch patients with similar health and SES [21]. Acknowledging the sensitivity of this topic, a 'prefer not to say' option is provided.

Patients will be scheduled for a clinical visit or not depending on the randomization group. The clinical visit contains of a check by the orthopaedic surgeon or orthopaedic resident and an X-ray. Additionally, a physical examination can be performed in case of concerns.

Information about the clinical visit will be collected. The patient or the HCP can also schedule a clinical visit in case of concerns, pain or symptoms. Information about these visits will also be collected.

Patients randomized to the active COD or RFU group will be asked to complete the questionnaires online or on paper. Completion time will be around 10-25 minutes. Table 1 depicts the data collection and assessments at baseline and during follow-up appointments.

Study data will be collected onto an electronic case report form (eCRF) in Castor EDC. The primary outcome will be measured at 11 years after surgery, i.e. 1 year after RFU or COD at 10 years. EQ-5D-5L and costs will be measured at 10 years after surgery (baseline), and at 3, 6, and 12 months after baseline in the RFU and active COD group. The other outcomes will be measured only at 10 years (baseline) and 11 years after surgery (end point).

Table 1: Overview of data collection and assessments.

	Baseline (10 years after surgery) (+/- 30 days)	In case of check-up on demand (10-11 years after surgery)	3 months (+/- 30 days)	6 months (+/- 30 days)	12 months (11 years after surgery) (+/- 30 days)
Clinical visit	X*	X			
Physical examination [#]	X	X			
X-ray	X*	X [#]			
Healthcare consumption	X	X	X	X	X
Questionnaires:**					
PROMIS	X				X
EQ-5D-5L	X		X	X	X
NPRS	X				X
NSRS	X				X
Costs	X		X	X	X

* Only RFU group

[#] In case of concerns

** Not for passive COD group

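### Detection of the primary complication endpoint differs by arm: X-ray changes that lead only to extra follow-up count, but only RFU patients have a scheduled X-ray

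*Protocol*

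**What the plan says.** Protocol section 8.1.1 defines the clinical primary endpoint as the number and type of complications, and explains these as "knee- or hip related complaints or changes on X-ray that lead to extra FU, a referral to another specialism or (surgical) intervention". It sets no threshold for symptoms or severity. Its examples include "loosening, malalignment or malposition of components, prosthetic wear, dislocation", some of which may be visible only on imaging.

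Section 8.3 describes the scheduled contact: "The clinical visit contains of a check by the orthopaedic surgeon or orthopaedic resident and an X-ray". In Table 1 the baseline visit and X-ray carry the footnote "Only RFU group". COD patients have a visit only on demand, and an X-ray then only if there are concerns. On timing, section 8.3 says: "The primary outcome will be measured at 11 years after surgery, i.e. 1 year after RFU or COD at 10 years". Table 1 lists no visit or X-ray at that point for any arm.

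The introduction (section 1) notes that "osteolysis (break down of bone tissue) and wear of the prosthesis can occur without symptoms" and names missed complications among the risks of moving to COD. Section 10.1 makes the complication count the primary comparison of RFU with active COD, using a Poisson mixed model. For the sample size, section 4.4 states "we assumed that the actual complication rate in both groups is 10" per cent.

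**The concern.** The randomised policy is also the instrument that detects the primary outcome. Take two patients with the same silent wear. Under RFU the change is seen, an extra check is booked, and a complication is recorded. Under COD nothing is recorded unless symptoms or an on-demand visit bring it out within the year. The missed finding, which the introduction gives as a reason for doing the trial, enters the COD count as no event.

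A lower count in COD could thus mean fewer complications, fewer detected complications, or less overdiagnosis. These readings carry different messages for the guideline, and the endpoint cannot tell them apart. The mixed model and its covariates cannot repair this, because undetected events never enter the data. Section 4.4 plans on equal rates in the two arms, which presupposes comparable detection or offsetting differences.

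**Working it through.** **1. The plan's own figure.** Inputs from section 4.4: rate p = 0.10 in both arms, margin m = 0.10, two-sided 95% interval, 80% probability that both limits lie inside the margin. With the 20% error split over the two limits:

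n = 2p(1−p)(z0.975 + z0.90)² / m² = 2 × 0.10 × 0.90 × (1.960 + 1.282)² / 0.01 ≈ 189.1, rounded up to 190.

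This matches the stated 190 per group. Allowing for 24% loss, 190 / 0.76 = 250. The sample size arithmetic is not in dispute.

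**2. Effect of extra findings in RFU only.** The protocol gives no figure for how many findings a scheduled X-ray adds, so x is an assumption. Let the observed rates be RFU = 0.10 + x and COD = 0.10, with n = 190 per arm and d = COD − RFU = −x. Then

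- SE = √{[(0.10 + x)(0.90 − x) + 0.10 × 0.90] / 190}
- P(upper limit below +0.10) = Φ((0.10 − d)/SE − 1.96)
- P(lower limit above −0.10) = Φ((0.10 + d)/SE − 1.96)
- P(both) = sum of the two − 1

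For x = 0.02: SE = √[(0.1056 + 0.0900)/190] = 0.0321. The upper term is Φ(0.120/0.0321 − 1.96) = 0.962, the lower is Φ(0.080/0.0321 − 1.96) = 0.703, and together they give 0.666.

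| Assumed x (points) | Upper limit excludes +10 | Lower limit excludes −10 | Both |
|---|---|---|---|
| 0 | 90% | 90% | 80% |
| 2 | 96% | 70% | 67% |
| 3 | 98% | 57% | 55% |
| 5 | 99% | 32% | 31% |

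The limit that matters for safety, ruling out an excess in COD, becomes easier to meet. The limit on the other side becomes harder.

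**3. Same question, other parametrisation.** Suppose the true rate is 10% in both arms and a share f of COD complications is never detected, so that COD is observed at 0.10(1 − f). The probability for both limits is 76%, 68% and 46% at f = 20%, 30% and 50%. The direction is the same, but the size depends on the model chosen.

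**4. Masking of a true excess (hypothetical).** Suppose COD truly had 20% against 10%. The chance that the upper limit nevertheless excludes a 10-point excess is 2.5% with equal detection, 7.7% at x = 2 and 25% at x = 5. In the other parametrisation it is 21% at f = 20% and 44% at f = 30%. Nothing in the protocol suggests a doubling. The scenario only shows which way the error runs.

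All of this uses a normal approximation for proportions, as section 4.4 implies. It does not model the Poisson analysis of section 10.1.

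**The case against.** **The size may be small.** The only related figure is in section 1: combining asymptomatic revision percentages with registry survival, COD may negatively affect 0.03–0.2% of patients. At x = 0.2 points the method above leaves the probability at about 80%. That stands as a low anchor. It concerns revision, however, and the endpoint is much wider because extra follow-up alone qualifies.

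**The direction is not certain.** A reader might infer that the comparison is certainly biased towards COD, and that the 10% assumption cannot hold if routine X-rays find anything. The documents do not support either. An on-demand visit for a complaint may itself be read as extra follow-up, while the same complaint settled at the routine visit may not count. Section 3 also warns that study contact and questionnaires may prompt patients to seek care. These could offset part of the difference. They are a second arm-dependent route of detection and do not restore comparability.

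**Extra findings are partly a real effect of RFU.** Section 1 mentions overdiagnosis and overtreatment under RFU, and a policy trial may legitimately count them. This is a good reason to keep the all-complications count. It does not help in telling overdiagnosis in RFU from a miss in COD.

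**Other outcomes help.** Silent disease that becomes symptomatic within the year counts in COD. Surgical interventions, registry revisions and patient-reported outcomes are secondary. They soften the problem without changing how the primary count reads.

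**Excluding what the scheduled visit found looks like a natural remedy.** It is not one. Only RFU patients can have such findings, so the exclusion removes events from one arm, including painful joints first reported at that visit. It would exchange a probable bias towards COD for one against it.

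**No equivalence rule is stated.** Section 4.4 calls its calculation a rough indication and section 10.1 gives no equivalence rule, so the percentages above describe the planning statement and not a declared decision rule.

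**Conclusion.** The point holds in a limited form. Detection of the primary complication endpoint differs by arm, because X-ray changes with no consequence beyond extra follow-up count and only RFU has a scheduled X-ray. As written, the primary count cannot separate fewer complications from fewer detected ones. The effect probably favours COD, but the net direction is not established.

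The size is not derivable from the protocol. Under an assumed 2 to 5 points of extra RFU yield on a 10% background, with 190 per arm, the planned 80% falls to about 67% to 31%. With a yield near the revision-based figure in section 1 it would hardly move. The endpoint definition and the visit schedule are both fixed in the protocol, so this is not a detail left to the SAP.

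**What to change.** 1. Keep the all-complications count as defined.
2. Classify every complication, in both arms, by route of detection (scheduled visit or X-ray, or on demand), by symptomatic or X-ray-only, and by consequence (extra follow-up, referral, intervention). Section 8.3 already collects visit type, reason and consequences. If symptoms at a routine visit cannot be read from those fields, one yes/no item in the eCRF is enough.
3. Report findings seen only at the scheduled X-ray separately, as RFU yield.
4. Prespecify a key supporting comparison of RFU with active COD that applies one rule to both arms, for example symptomatic complications whichever visit brought them out, or complications leading to intervention. Do not drop events because they were found at the RFU visit. This lessens the dependence on detection without removing it: a scheduled visit can still elicit complaints, and a silent finding can still lead to surgery.
5. State in the protocol that a lower all-complications count in COD will not by itself be read as evidence of safety, and that the safety conclusion is limited to clinically manifest complications within 1 year.

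The cost is a wording change, a classification largely from existing fields, slightly more analysis, and a narrower claim. No visit, X-ray or care pathway changes. It should be settled before outcome data are seen.

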8.1.2 Secondary study parameters/endpoints (if applicable)

- PROMIS physical function
- Number and type of surgical interventions (like DAIR, partial component exchange, revision surgery (full prosthesis replacement), irrigation and debridement (without component retention))
- Additional healthcare consumption related to THA or TKA FU (like clinical visit, telephone consultations, X-ray, CT scan, MRI scan, laboratory tests)
- Costs (based on electronic patient records and additional questionnaires, including all visits to healthcare professionals outside the hospital)
- Numeric Pain Rating Scale (NPRS)
- Numeric Satisfaction Rating Scale (NSRS)
- Health related quality of life (EQ-5D-5L)

For the passive COD group only available data from the EPD and LROI will be collected.

8.1.3 Other study parameters (if applicable)

- Patient characteristics (like age, gender, BMI, ASA score, ethnicity, employment status, home-hospital distance and educational level)

- Surgical information of primary arthroplasty (like surgery date, approach, type of prosthesis, fixation method, surgical duration, and intra-operative complications)
- Postoperative characteristics (like length of stay, in-hospital complications and discharge destination)
- Healthcare consumption, complications, and surgical interventions from the time of THA/TKA up to 10 years postoperatively

8.2 Randomisation, blinding and treatment allocation

Participants are randomly assigned in a 1:1:1 ratio to one of the three groups: RFU, active COD or passive COD. In order to do so, randomisation takes place in two steps and will be done using Castor EDC.

First, patients will be randomly allocated in a 1:2 ratio to the active group and the passive COD (intervention) group, with use of dynamic block designed randomisation with blocks of 6, 9 and 12. From the passive COD group, 25 THA and 25 TKA patients will be randomly selected. Patients in the passive COD group are not informed about the study and are blinded. Only data from EPD and LROI register will be collected.

Second, patients who are not placed in the passive COD group will be informed about the study. After informed consent, they will be randomly allocated in a 1:1 ratio to group 1 (RFU, control) or group 2 (active COD, intervention) with use of dynamic block designed randomisation with blocks of 4 and 6 and stratification by center and procedure (TKA or THA). There patients are not blinded. Inclusion will stop once the groups are filled.

8.3 Study procedures

This study will be conducted in 10 Dutch hospitals across the Netherlands. Patients will be recruited using the LROI register and EPD. After inclusion, baseline characteristics will be obtained from the EPD and LROI register. Information on patient background will be collected to explore potential differences in follow-up needs, including among patients with different ethnic backgrounds. Previous research shows that people with a migrant background visit specialists and hospitals less often than native Dutch patients with similar health and SES [21]. Acknowledging the sensitivity of this topic, a 'prefer not to say' option is provided.

Patients will be scheduled for a clinical visit or not depending on the randomization group. The clinical visit contains of a check by the orthopaedic surgeon or orthopaedic resident and an X-ray. Additionally, a physical examination can be performed in case of concerns.

Information about the clinical visit will be collected. The patient or the HCP can also schedule a clinical visit in case of concerns, pain or symptoms. Information about these visits will also be collected.

Patients randomized to the active COD or RFU group will be asked to complete the questionnaires online or on paper. Completion time will be around 10-25 minutes. Table 1 depicts the data collection and assessments at baseline and during follow-up appointments.

Study data will be collected onto an electronic case report form (eCRF) in Castor EDC. The primary outcome will be measured at 11 years after surgery, i.e. 1 year after RFU or COD at 10 years. EQ-5D-5L and costs will be measured at 10 years after surgery (baseline), and at 3, 6, and 12 months after baseline in the RFU and active COD group. The other outcomes will be measured only at 10 years (baseline) and 11 years after surgery (end point).

Table 1: Overview of data collection and assessments.

	Baseline (10 years after surgery) (+/- 30 days)	In case of check-up on demand (10-11 years after surgery)	3 months (+/- 30 days)	6 months (+/- 30 days)	12 months (11 years after surgery) (+/- 30 days)
Clinical visit	X*	X			
Physical examination [#]	X	X			
X-ray	X*	X [#]			
Healthcare consumption	X	X	X	X	X
Questionnaires:**					
PROMIS	X				X
EQ-5D-5L	X		X	X	X
NPRS	X				X
NSRS	X				X
Costs	X		X	X	X

* Only RFU group

[#] In case of concerns

** Not for passive COD group

In case of a clinical visit information will be collected about the visits, like whether the visit was a routine visit or on demand, the reason for the visit, date of the visit, consequences of possible findings (like change in policy and secondary health consumption). In case of a routine visit, we will collect data whether the patient cancelled the appointment and the reason of cancellation.

PROMIS physical function will be obtained using the short form (SF) [22]. In case hospitals already use computer adaptive testing (CAT) of PROMIS physical function in clinical practice, this will be used. Version 10b will be used. The SF PROMIS physical function consists of 10 questions and is expressed by raw summed score ranging from 10 to 50, which can be converted to a T-score and SE. The T-score is a standardized score with a mean of 50 and a SD of 10.

EuroQol-5D (EQ-5D-5L) is a general health-related quality of life questionnaire and consists of five questions regarding mobility, self-care, usual activities, pain/discomfort and anxiety/depression and one visual analog scale (VAS) to document the perceived quality of life [23]. The quality of life is described by 2 scores, the index value, which range from 0 to 1, and the VAS score, which range from 0 to 100. For both scores applies the higher the better. Numeric Rating Scale for pain (NPRS) is a scale ranging from zero to ten on which patients can score their pain [24]. It is a widely used instrument in varying populations due to its ease of administration and clinical relevance to the patient. The lower the score, the better.

Numeric Rating Scale for satisfaction (NSRS) will be measured by a single question: "How satisfied are you with the results of the treatment?" The patient will answer this question with a NRS scale ranging from zero to ten. The higher the score, the better.

Health consumption and costs will be measured using the EPD. Health consumption includes both the primary outcomes clinical visits and X-rays, as well as additional health care use, including telephone consultations and scans. The LROI register will be used to collect data about revision surgery. A questionnaire will be used to get more insight in the health consumption and costs which cannot be obtained from the EPD. This questionnaire is made in collaboration with a HTA expert and patient representatives.

